tDCS. Multiple steps will be taken to decrease the risks of tDCS. This includes using an electrical dose titration procedure with ongoing adverse event assessment and subject self-rating of discomfort which will guide whether dose increases occur in order to minimize discomfort and risk. This will also allow us to meet a goal of administering a dosage that is the minimum electrical dosage that engages our target to minimize risk. Also, because the

risks of tDCS which we propose to administer are not well characterized we plan to administer treatment for relatively brief periods (up to 10 minute stimulation sessions) and not administer treatments that have an impact on our target neural circuitry as indicated by pupillometry more frequently than weekly. Further, we may monitor ECG and breathing throughout and after all tDCS treatments to further minimize risks. Subjects will also be instructed to indicate if they have pain or discomfort and treatment will be stopped immediately if requested by a subject. Also, electrode sites will be checked for any skin abrasions prior to each treatment, as the presence of these increases the risk of skin burns. Treatment is not given if there are skin abrasions at the electrode sites. We will also carefully monitor subjects for adverse events after every stimulation with the SAFTEE tool and specifically ask them about the presence of the following side effects: itchiness, dizziness, lightheadedness, blurred vision, or headache. If any of these are answered positively, the duration of the symptom/s will be monitored and if it does not dissipate within an hour, which is typical of the symptom/s will be monitored and if it does not dissipate within an hour, which is typical of tDCS, the participant will be assessed by a medical practitioner and appropriate care provided.

Pupillometry. In order to minimize risks of pupillometry, sessions will be kept as short as possible and there will be a study physician with all subjects during the procedure. Subjects will be assessed for adverse events and if they are detected, appropriate care will be made available.

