Because of the novel nature of the proposed work and that the adverse effects profile of the form of tDCS we propose to study is not well-documented, we have set up a Data and Safety Monitoring Board (DSMB) for both the R21 and R33 phases of the proposed effort. The individuals who serve on the DSMB were chosen in conjunction with NIH Program staff and have extensive experience conducting clinical trials and are highly familiar with the proposed methodology. The DSMB will convene every 6 months to review ongoing study procedures, discuss AEs and other safety issues, and to evaluate ongoing methods for maintaining data integrity and confidentiality. They will be provided with a summary of all AEs, outcome data, progress data and subject ratings of treatment tolerability prior to each meeting. They will play a critical role in working with the PI and NIH Program to assess whether the "Go-No-Go" criteria are met for proceeding to the R33 phase. If a decision is made to proceed, they will then monitor the R33 study. Should the DSMB members develop any concerns on the basis of information provided to them by the PI, they may request to examine hard or electronic copies of the participants' research records or other information. In transferring information to the DSMB participants' identities will be protected by transferring only data that are de-identified (hard copies) and/or encrypted (electronic data). In considering the frequency of meetings, we have tried to strike a proper balance between maintaining participant safety and the integrity of the study, and the consequent time and workload. Traditionally, DSMBs convene once a year. However, given the novel nature of this trial and that the risks of the form of tDCS we are administering are not well documented it was felt that every 6 month meetings were appropriate. After each meeting the DSMB will compile the information gained from the monitoring activities and subsequently prepare a report summarizing findings. Also included in the report is their recommendation to continue or discontinue the study. This report is completed and delivered to the NIH and the PI. If the DSMB concludes that the study should be terminated, this opinion will be conveyed to the UCSF business officials as well in the case of this latter type of recommendation. Subsequently the PIs, appropriate business officials at UCSF, and NIH Program will likely discuss the matter further before a final decision regarding study termination is made.

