
Local Monitoring of Subjects, Rules for Withdrawing Participants from Study Interventions, and Safety Stopping Rule: All subjects who undergo tDCS treatments will be carefully monitored locally by one of the study physicians. A study physician will be in the room with all subjects when any study procedures are carried out. There will be close monitoring of the tolerability of each of the tDCS electrode configurations studied. In order to determine the tolerability of particular tDCS electrode placement and electrical stimulus intensities, subjects will rate their discomfort immediately after each tDCS stimulus on a 5-point Likert scale that has been widely used to assess the tolerability of procedures including colonoscopy, nasogastric tube insertion, burn dressing application, and orthodontic procedures. The anchors are: 0="No Discomfort", 1="Minimal Discomfort", 2="Mild Discomfort", 3="Moderate Discomfort", and 4="Severe Discomfort". We employ a cutoff of no more 2 as an indicator of acceptable tolerability. We will employ the following stopping rule for each tDCS configuration test: "If any tDCS electrode configuration is rated at 3 or higher by 3 subjects, all testing with that electrode configuration will cease." In addition, if there is an SAE consisting of the development of new neuropsychiatric symptoms, the study will be halted until the cause of the symptoms is ruled not to be due to the study and, if such an event is determined to be related to the study, the study will not be restarted until modifications to the study methods are made that reduce the risk of such an event recurring based on a review and approval by the DSMB. Any subject who rates tolerability as 3 or greater for any electrode configuration will be withdrawn from further participation. Subjects will be informed that, at any time, they may request to the study physician that study procedures stop and this will occur. This includes that they will specifically be told that they should indicate if they would like tDCS stimulation to

stop during stimulation and it will cease and that they should indicate if they would like to stop CO2 inhalation during the CO2 inhalation procedure and that procedure will immediately be terminated.

Plan for Conducting and Reporting Interim Analysis and Stopping Rule

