The DSMB will convene every 6 months to review ongoing study procedures, discuss AEs and other safety issues, and to evaluate ongoing methods for maintaining data integrity and confidentiality. They will be provided with a summary of all AEs, outcome data, progress data and subject ratings of treatment tolerability prior to each meeting. In transferring information to the DSMB participants' identities will be protected by transferring only data that are de-identified (hard copies) and/or encrypted (electronic data). After each meeting the DSMB will compile the information gained from the monitoring activities and subsequently prepare a report summarizing findings. Also included in the report is their recommendation to continue or discontinue the study. This report is completed and delivered to the NIH and PI. If the DSMB concludes that the study should be terminated, this opinion will be conveyed to the UCSF business officials as well. In the case of this latter type of recommendation. Subsequently the PIs, appropriate business officials at UCSF, and NIH Program will likely discuss the matter further before a final decision regarding study termination is made. The members of the DSMB are: [name] MD (Chairman), Professor of Psychiatry, Emory University who has extensive experience in carrying out research studies involving BrainStimulation therapies; [name], Professor of Psychiatry University of Iowa who has extensive experience in carrying out studies employing pupillometry in assessing psychiatric disorders; and [name]., Professor of Biostatistics at Wake Forest University who has extensive experience in Biostatistics.

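### The only study-level halt triggered by an SAE covers new neuropsychiatric symptoms, so a related SAE of another kind triggers no stated pause before the next subject

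*Combined protocol and SAP*

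**What the plan says.** The safety rules are in section 13.2, in the paragraph on local monitoring, withdrawal and stopping. The study-level rule reads: "if there is an SAE consisting of the development of new neuropsychiatric symptoms, the study will be halted". The halt lasts until the study is ruled out as the cause. If the event is found to be related, "the study will not be restarted until modifications to the study methods are made that reduce the risk of such an event recurring", and the DSMB must review and approve those changes.

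The other stops in that paragraph rest on discomfort or on the subject's wishes. A subject who rates discomfort at 3 or more is withdrawn. For a whole electrode placement the rule is: "If any tDCS electrode configuration is rated at 3 or higher by 3 subjects, all testing with that electrode configuration will cease". A subject may also ask to stop at any time.

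Supervision is close. "A study physician will be in the room with all subjects when any study procedures are carried out". Section 12.3 adds: "We will also carefully monitor subjects for adverse events after every stimulation with the SAFTEE tool". On oversight, section 13.2 says: "The DSMB will convene every 6 months to review ongoing study procedures, discuss AEs and other safety issues". Of the DSMB's material it says: "They will be provided with a summary of all AEs, outcome data, progress data and subject ratings of treatment tolerability prior to each meeting". Of the DSMB's report, sections 13.2 and 13.4 say: "Also included in the report is their recommendation to continue or discontinue the study". Section 13.2 also sends an interim analysis to the DSMB after each R21 cohort.

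Section 8.25 equates testing the R21 hypotheses with testing the Go-No-Go criteria for R33. One of these, Hypothesis 2b, requires that active tDCS cause no related adverse effect above mild severity.

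**The concern.** The halt rule is well built: stop first, establish the cause, and do not restart after a related event without DSMB approval. Its trigger is one class of SAE. The plan watches for harms outside that class. Section 12.3 provides continuous ECG and breathing monitoring during CO₂ inhalation and checks the skin under the electrodes because abrasions raise the burn risk. Section 8.4 gives tDCS during the last 5 minutes of the 20-minute CO₂ inhalation. A serious event picked up by that monitoring has no study-level consequence written down.

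The subjects are healthy volunteers, and section 13.2 itself says the adverse-effect profile of this form of tDCS is not well documented. For a related SAE that is not neuropsychiatric, whether the next subject is treated before anyone outside the study team has looked at the event is left to judgement between scheduled DSMB meetings.

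**Working it through.** The plan gives no figure to reproduce and no arithmetic decides the point. The check is to take every provision that could act after a related, non-neuropsychiatric SAE and ask what triggers it and whether it pauses the study before the next subject.

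| Provision (section) | Trigger | Effect | Study-level pause after such an SAE? |
|---|---|---|---|
| Study halt (13.2) | SAE of new neuropsychiatric symptoms | Study stops; restart after a related event needs DSMB approval | No: other event type |
| Subject withdrawal (13.2) | Discomfort rating of 3 or more | That subject leaves | No |
| Configuration stop (13.2) | Such ratings from 3 subjects | That electrode placement is dropped | Not on one event |
| Stop on request (13.2) | Subject asks | That procedure ends | No |
| Physician present; SAFTEE; care offered (13.2, 12.3) | Continuous, or after each stimulation | Detects and treats the affected subject | No |
| Titration guided by adverse events and discomfort (12.3) | Within-subject findings | Governs that subject's dose | No |
| Standard procedures for adverse events (12.3) | Any recorded adverse event | Not described | None stated |
| Routine DSMB review (13.2, 13.4) | Six-month calendar | Report with a recommendation | Not before the next meeting |
| Cohort interim analyses (13.2) | End of a cohort | Tolerability and pupil results go to the DSMB | No |
| Go-No-Go, Hypothesis 2b (8.25) | Decision on R33 | Related adverse effect above mild fails the criterion | No: a gate between phases |

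Two cases show how the rules work.

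1. A related arrhythmia during the overlap of CO₂ and tDCS. The discomfort scale asks about discomfort, so the rating may stay at 2 or below. Then no withdrawal, configuration or study rule is met. The physician treats the subject, and the event appears in the next DSMB summary. If it is attributed to active tDCS in R21, it also counts against Hypothesis 2b when the phase decision is made.
2. A serious, painful burn. It would plausibly be rated 3 or more, so that subject is withdrawn and the event counts toward the configuration stop. That stop needs 3 subjects, so 3 − 1 = 2 more such ratings are required before testing of the placement ends.

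Once a single placement is in use (the last 10 R21 subjects and all of R33), the configuration stop would in effect stop the study. It would still need three discomfort ratings, and one SAE would not be enough.

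**The case against.** The best case for the plan has four parts.

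- **The risk looks low.** Section 9.4 reports no serious adverse effect in over 33,200 sessions of conventional tDCS, and the stimulation given with CO₂ lasts 5 minutes. The systolic rise of about 18 points in section 12.2 is an expected effect of CO₂, and burns are mentioned while describing the precaution against them. This stands as a reason for modest severity. It does not settle the matter, because section 13.2 treats the risks of this form of tDCS as not well documented. If SAEs are rare, the wider rule will seldom be used.
- **There is a broad safety gate.** Hypothesis 2b covers related adverse effects of any kind, the DSMB helps assess the Go-No-Go criteria, and R33 needs a fresh IRB submission (section 8.4). This stands, and it limits the concern for R33. It does not act between subjects within a phase.
- **Physicians on site would pause anyway.** Probably so. The sponsor nevertheless chose to remove that discretion for one class of SAE.
- **Unseen material may cover it.** The full DSMB charter, the IRB's reporting policy and the standard procedures of section 12.3 are not set out. This stands: the claim is only that no pause is stated here.

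Two stronger readings are tempting. A reader might infer that a related SAE outside the neuropsychiatric class meets none of the plan's stops. The burn example shows otherwise, so the claim is confined to a study-level pause. A reader might also infer that the CO₂ cohort opens without the DSMB being in a position to object. The documents do not support that: the interim analyses go to the DSMB, which also receives all adverse events at routine meetings and may ask for records.

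**Conclusion.** The point holds in a narrow form. The only study-level halt triggered by an SAE is limited to new neuropsychiatric symptoms, and these documents state no study-level pause after a related SAE of another kind. This goes beyond missing detail, because a halt rule is written and its trigger is narrower than the hazards the plan monitors. The existing protections are substantial, and the remedy is a cheap improvement.

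Its size cannot be given as a probability or a number of subjects harmed, because the documents contain no SAE rate for this form of tDCS. A reader might take the number of subjects enrolled between DSMB meetings as a measure of the harm. It is not one: enrolment includes people who fail screening, and exposure without an event rate says nothing about risk. Nor do the documents suggest that the investigators intend to carry on after a serious event.

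The conclusion assumes that the charter and IRB policy add no pause. If either does, a cross-reference in section 13.2 closes the point.

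**What to change.** In the safety stopping paragraph of section 13.2, keep the neuropsychiatric halt exactly as written, including that it applies before relatedness is settled. Add that any other SAE rated possibly, probably or definitely related to tDCS or CO₂ also halts the study, and that restart needs DSMB review and approval under the same mechanism. Name CO₂ explicitly, since Hypothesis 2b is worded around active tDCS. Apply the rule in R21 now and carry it into the R33 IRB submission.

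The change uses the existing DSMB, the existing restart process and the relatedness grades of section 8.25. It alters no endpoint, sample size or analysis. Its cost is an occasional ad hoc DSMB call and a short pause, some of which will follow events later judged unrelated. Including SAEs rated only possibly related is a choice, and the sponsor could defend a somewhat higher threshold if it is written down.

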14.0 Confidentiality, Privacy, and Data Security

14.1 PROTECTING PRIVACY: Indicate how subject privacy will be protected:

-
- Conduct conversations about the research in a private room
 - Ask the subject how they wish to be communicated with – what phone numbers can be called, can
 - messages be left, can they receive mail about the study at home, etc.
- Take special measures to ensure that data collected about sensitive issues do not get added to
- their medical records or shared with others without the subject's permission Other methods (describe below)

14.2 SENSITIVE DATA: Do any of the instruments ask about illegal or stigmatized behavior:

-
-

Yes No

IMPORTANT NOTE: Indicate in the consent form what kinds of sensitive information will be collected.

14.3 CONSEQUENCES OF A LOSS OF PRIVACY OR CONFIDENTIALITY: Could a breach of privacy or confidentiality result in any significant consequences to participants, such as criminal or civil

liability, loss of state or federal benefits, or be damaging to the participant's financial standing, employability, or reputation:

Yes No

14.4 EXTRA CONFIDENTIALITY MEASURES: Explain any extra steps that will be taken to assure confidentiality and protect identifiable information from improper use and disclosure, if any:

14.5 * REPORTABILITY: Do you anticipate that this study may collect information that State or Federal law requires to be reported to other officials, such as elder abuse, child abuse, or threat to self or others: (REQUIRED)

Yes No

14.6 CERTIFICATE OF CONFIDENTIALITY: Will this study obtain a Certificate of Confidentiality:

Yes No

14.7 SHARING OF RESEARCH RESULTS: Will there be any sharing of **EXPERIMENTAL research test results with subjects or their care providers:**

Yes No

14.8 * IDENTIFIERS: Will any personal identifiers be collected: **(REQUIRED)**

Yes No

Check all the identifiers that may be included:

- Names
- Dates
- Postal addresses
- Phone numbers
- Fax numbers
- Email addresses
- Social Security Numbers*
- Medical record numbers
- Health plan numbers
- Account numbers
- License or certificate numbers
- Vehicle ID numbers
- Device identifiers or serial numbers
- Web URLs
- IP address numbers
- Biometric identifiers
- Facial photos or other identifiable images
- Any other unique identifier

* Could study records include ANY photos or images (even 'unidentifiable' ones):
(REQUIRED)

Yes No

14.9 DATA DISCLOSURE: Will identifiable information be shared with outside groups:

Yes No

14.11 * DATA COLLECTION AND STORAGE: (check all that apply): **(REQUIRED)**

Collection methods:

- Paper-based (surveys, logs, diaries, etc.)
- Electronic case report forms (CRFs), such as OnCore or another clinical trial management portal
- Web-based online surveys or computer-assisted interview tool
- Mobile applications (mobile or tablet-based)
- Wearable devices
- Audio/video recordings

Other:

* Data will be collected/stored in systems owned by (check all that apply): **(REQUIRED)**

- UCSF
- SF VAMC
- Amazon (Amazon Cloud)
- Other academic institution
- 3rd party vendor (business entity)
- Other (explain below)

14.12 DATA SECURITY: Indicate how data are kept secure and protected from improper use and disclosure (check all that apply): NOTE: Whenever possible, do not store subject identifiers on laptops, PDAs, or other portable devices. If you collect subject identifiers on portable devices, you MUST encrypt the devices.

- Data are stored securely in My Research
- Data are coded; data key is destroyed at end of study
- Data are coded; data key is kept separately and securely
- Data are kept in a locked file cabinet
- Data are kept in a locked office or suite
- Electronic data are protected with a password
- Data are stored on a secure network
- Data are collected/stored using REDCap or REDCap Survey
- Data are securely stored in OnCore

14.13 * DATA SECURITY: Confirm below that you will keep data confidential: (REQUIRED) I will keep any data sets that include identifiers secure and protected from improper use and disclosure by using methods such as:

- Physical Security – Keeping data in locked file cabinets, locked offices, locked suites, and physically securing computers and servers.
- Electronic Security – Following [UCSF minimum security standards for electronic information resources](#), which includes (but is not limited to): not storing identifiers on portable devices like laptops or flash drives if they are unencrypted, encrypting portable devices, and storing data in password-protected files and on secure networks.

Yes

14.15 HIPAA APPLICABILITY: Study data will be:

- Derived from the Integrated Data Repository (IDR) or The Health Record Data Service (THREDS) at SFGH
- Derived from a medical record (e.g. APeX, OnCore, etc. Identify source below)
- Added to the hospital or clinical medical record
- Created or collected as part of health care
- Obtained from the subject, including interviews, questionnaires
- Obtained ONLY from a foreign country or countries
- Obtained ONLY from records open to the public
- Obtained from existing research records
- None of the above

15.0 Financial Considerations

15.1 * PAYMENT: Will subjects be paid for participation, reimbursed for time or expenses, or receive any other kind of compensation: (REQUIRED)

Yes No

15.2 PAYMENT METHODS: Subjects payment or compensation method (check all that apply):

Payments will be (check all that apply):

- Cash
- Check
- Gift card
- Debit card
- UCSF Research Subject Payment Card
- Reimbursement for parking and other expenses
- Other:
-

15.3 PAYMENT SCHEDULE: Describe the schedule and amounts of payments, including the total subjects can receive for completing the study:

- If there are multiple visits over time, explain how payments will be prorated for partial completion
- If deviating from recommendations in Subject Payment Guidelines, include specific justification below

Participants will be provided monetary compensation to cover the time and effort they will invest completing the various study procedures. All but the last 10 subjects will receive up to \$150 for completing the study which involves a screening session plus two visits. The last 10 subjects will receive \$200 for completing the study, which involves a screening session plus three visits (\$50 per visit) where tDCS will take place.

15.4 COSTS TO SUBJECTS: Will subjects or their insurance be charged for any study activities:

Yes No

